## WILLOW Full RCT Patient Protocol

standard therapy and computer-assisted therapy aided by our newly developed software called WILLOW. If you decide to participate in this study, you will be asked to meet with a therapist for 12 weeks. Your therapist has already been assigned to one of the two study conditions [let them know what condition they were assigned], which means you are also in the [standard care, WILLOW] condition with them.

**<<for RA: if not yet assigned to therapist, describe both conditions. If assigned to therapist and we know their condition, describe only the condition they are assigned to unless they want to hear about both conditions.>>**

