## WILLOW Full RCT Patient Protocol

The information you provide during this study will be used for research purposes only; it will not be shared with your therapist or treatment team. Your treatment and your participation in our study are separate but parallel activities. You are doing them at the same time but there will not necessarily be any cross over between the two EXCEPT for during the research appointments I just described to you where we'll ask about how sessions are going and what type of activities you do in session, etc. Everything you do for the research will be either on the phone or on SurveyMonkey, where the surveys are located. Everything else <>for WILLOW patient participants specify measures, videos, worksheets, etc in WILLOW>> would be for your therapy separate from the research. If you ever need clarification, please ask your provider or contact us.

As you know, the length of research-based treatment is 12 weeks. After the 12-week period, you and your therapist or clinic will decide what your next steps for treatment will be. If you have questions about this, we encourage you to talk with your therapist or clinic before enrolling in the study. While the research trial is 12 weeks, this does not mean you must quit treatment after 12 weeks or that you are obligated to continue treatment for 12 weeks. If more treatment is needed after the 12-week period, you will work with your therapist and the clinic to decide how to proceed. If you decide to stop treatment before the 12 weeks of your study participation are over, we ask that you still complete the online surveys and phone calls, regardless of whether or not you are still receiving treatment from your study therapist.

As compensation for your study participation and time involved in completing the online surveys and phone calls, you will receive \$40 for each of your Week 4 and Week 8 surveys, and \$60 for your Week 12 survey, for a total of \$140 if you complete all study procedures. The payment will be coming from Chase Bank so be sure to keep an eye out for envelopes from Chase when the time comes.

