- You will be randomized to one of two conditions: the WILLOW condition or standard care condition.
- If you are randomized to the WILLOW condition, you will be asked to use a computer in session to guide you through conducting Behavioral Activation for the treatment of depression.
- If you are randomized to the standard care condition, you will be asked to conduct treatment as you normally would.
- In both cases, we will ask that you meet with 2-5 research patients for 12 weeks each. You can choose to treat as many study patients as your schedule allows. Patients that

WILLOW Full RCT Therapist Protocol

are enrolled in the study with you will need to be new patients to your clinic and must not have received treatment from you previously.

- You can still use WILLOW with your patients who are not involved in the research study.
- Participants in both conditions will be asked to complete one online survey before starting the study (baseline) and another set of online surveys with a brief telephone interview after 4, 8 and 12 weeks for each research patient they treat. You will be compensated \$50 for each 4 week and 8 week survey, and \$60 for each 12 week survey you complete.
- You will be eligible to obtain free access to WILLOW for 12 months after the completion of your participation, which involves successfully recruiting at least 1 study patient and completing all assessments for that patient.

Does this sound like something you would be interested in?

If no, thank them for their time and hang up.

If yes, proceed to the next section.

Awesome! The next step would be for you to read and sign a consent form.

The entire process takes about 15-20 minutes. I will send you an email shortly that contains the link to the consent form and we ask that you complete it within the next two days. After completing the consent form, we will randomize you to either the WILLOW condition or the standard care condition and follow up with orientation brief call to explain the next steps.

Do you have any last questions for me?

Thank you so much for your interest in our research. Please don't hesitate to contact us if you have any questions as you are reviewing the consent form. Have a great day!

Step 3: Send Consent Survey

1. Send therapist consent survey email
2. Log date consent sent in the [Summative Tracking DB](#)

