If your patient exits therapy before the 12-week study trial is over, that is okay. Neither the patient nor the therapist will be removed from the study. If this happens with any of your patients, we will still ask both you and your patient complete your post surveys and you will be paid in full upon completion of the surveys. Similarly, if any sessions are skipped or rescheduled, we will still ask you both to complete the assessments as planned.

After the week 12 survey is completed, you and your clinic will decide the next steps for the patient and if more treatment is indicated or requested, whether or not you continue with the patient outside of the study or if they will be assigned to a non-research therapist.

Do you have any questions at this point?

Describe goal of Full RCT (for both conditions):

- To give you an overview, the purpose of this full randomized controlled trial (RCT) is to test WILLOW, our computer-assisted therapy tool, and how it can be used to assist therapists to treat their patients who are experiencing depression. Additionally, we will also assess the wellbeing of both you and your patient. .

Any questions?

Describe Next Steps:

For CAU Condition Only: Skip to Step 9

<<For pilot WILLOW therapists briefly note:

- The account activation link no longer expires, but please ask your research patients to try to complete the activation as soon as possible.
- Email reminders for measures are sent the day before the due date and there is no email reminder for homework items you manually entered in WILLOW.

WILLOW Full RCT Therapist Protocol

- New feature: RCI, reliable change index, that tells you whether the change in score for a particular measure is significant.
- Your patients using WILLOW (either research patients or non-research patients) can login to WILLOW anytime to complete measures or homework, once they have activated their account, and do not need to wait for an email to prompt them.
- If they are experiencing technical difficulties, please direct them to contact our customer support ([contact]). They can also use the green Feedback & Support tab in WILLOW to contact us.

Skip to Step 9 or schedule a refresher review if needed: Now, how are you feeling about using WILLOW? Do you feel that you would need another review with me to refresh your memory?>>

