PracticeGround: Transforming Training and Delivery of Mental Health EBPs

NCT02314624 | Statistical Analysis Plan | February 8, 2020

Analysis Strategy

We conducted all analysis in IBM SPSS V19. We used the Generalized Linear Model to examine the between-condition change over time on study outcomes. The effects of primary interest were those reflecting the effects of WILLOW. For outcomes measured at baseline and follow-up points, that was the Time X Condition effects (measuring between-condition change from baseline). For outcomes measured only at follow-up points (e.g., therapeutic alliance and use of evidence-based therapy tasks), that was the Condition effects since they would represent average between-condition differences during the time patients received services. As previously mentioned, providers completed questionnaires for each study patient they treated. Hence, the provider sample size reflects the number of patients they answered about, not the number of providers. Several providers participated in the study concurrently with multiple patients. Patients were included in the analyses only if they attended five or more sessions with a participant provider.

Preliminary analyses provided important information guiding our strategy. First, we found no statistically significant differences between conditions on baseline measures. Second, we computed the design effects due to this nested design to determine the extent to which the intraclass correlation due to clustering and size of the cluster affected the analyses. Design effects ranged up to 1.8. Because all were under 2.0, we did not adjust analyses to account for clustering effects (Muthén & Satorra, 1995). For providers meeting participating in both studies, we used their Study 1 data for outcomes except for outcomes measured only in Study 2. For those outcomes, we used their Study 2 data.

References

Muthén, B.O. & Satorra, A. (1995). Complex sample data in structural equation modeling. *Sociological Methodology*, 25, 267-316. doi: 10.2307/271070

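### The only stated patient analysis set requires five or more attended sessions, a filter applied after therapist randomisation that drops follow-up the protocol asks for

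*SAP*

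**What the plan says.** The SAP (Analysis Strategy) gives one patient inclusion rule: "Patients were included in the analyses only if they attended five or more sessions with a participant provider". It gives no reason for choosing five and names no all-allocated set, no analysis without the filter and no missing-data method. The main effect is Time X Condition for outcomes with a baseline. For outcomes measured only at follow-up it is the Condition effect, described as "average between-condition differences during the time patients received services".

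The protocol defines no analysis set, but it does fix allocation and follow-up:

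- Therapists are told at consent (Therapist Protocol, Step 2): "You will be randomized to one of two conditions: the WILLOW condition or standard care condition".
- Patients are told at their own consent call (Patient Protocol, Step 3): "Your therapist has already been assigned to one of the two study conditions".
- Patients who stop treatment early are told in the same call: "we ask that you still complete the online surveys and phone calls, regardless of whether or not you are still receiving treatment".
- Therapists are told about patients who leave early (Therapist Protocol, Step 7): "Neither the patient nor the therapist will be removed from the study". The same step adds that "if any sessions are skipped or rescheduled, we will still ask you both to complete the assessments as planned".

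**The concern.** Sessions attended is a post-randomisation variable. The arm could plausibly affect it, although the documents do not show that it does. WILLOW therapists are asked to use the Behavioral Activation module every week and to assign weekly questionnaires, while standard-care therapists treat as usual. Therapists know their arm, and patients with an assigned therapist are told it. If the share of patients falling short of five sessions differs by arm, or if the reasons for falling short differ, the retained groups are no longer comparable and a difference can appear with no true effect.

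The rule also sets aside data that the trial went out of its way to request. Because the documents do not contradict each other outright, this is a mismatch between data sought and data analysed. At stake is whether the result can be read as the effect of allocating therapists to WILLOW or only as a comparison of patients who stayed for at least five sessions.

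**Working it through.** **1. Timing.** Therapists are randomised after their own consent (Therapist Protocol, Steps 2 to 5), and a patient assigned to a therapist enters that therapist's arm. Attendance comes later. With weekly sessions, and counting study sessions only, the fifth falls at about Week 4 at the earliest. The exact session count is collected from the therapist at the final assessment (Therapist Protocol, Steps 6 and 7).

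**2. Who is dropped.** A patient who stops after five sessions, or skips some but still reaches five, is kept. A patient who stops or skips and never reaches five is excluded, even if every survey was returned. The documents do not say how many such surveys came back.

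**3. No plan figure to reproduce.** The documents give no sample size, outcome SD, attendance figures or exclusions by arm. What follows is illustration on assumed inputs.

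**4. Model.** Assume no true effect. Let attendance propensity be a latent normal variable, with the lowest fraction p falling short of five sessions. Let r be the correlation between that propensity and a good outcome. Then

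- shift in the retained mean, in SD = r × φ(z_p) / (1 − p)
- spurious between-arm difference = shift(p1) − shift(p2)

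The factor φ(z_p)/(1 − p) is 0.2743 at p = 15%, 0.3500 at 20%, 0.4237 at 25%, 0.4967 at 30%, 0.5698 at 35% and 0.6439 at 40%.

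**5. Unequal exclusion, r = 0.3 to 0.5**

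| Excluded, one arm vs other | Factor difference | Bias in SD | Points if change SD is 6 |
|---|---|---|---|
| 25% vs 20% | 0.074 | 0.022 to 0.037 | 0.13 to 0.22 |
| 35% vs 25% | 0.146 | 0.044 to 0.073 | 0.26 to 0.44 |
| 30% vs 15% | 0.222 | 0.067 to 0.111 | 0.40 to 0.67 |
| 40% vs 20% | 0.294 | 0.088 to 0.147 | 0.53 to 0.88 |

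Over assumed change SDs of 4 to 8, the smallest gap gives 0.09 to 0.29 points and the largest 0.35 to 1.18. A simulation at SD 6 with 2,000,000 draws per arm agreed with the formula to within 0.01 points.

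**6. Equal exclusion, 25% in each arm.** With the same r in both arms the bias is 0. With r = 0.3 against 0.2 it is 0.1 × 0.4237 = 0.042 SD. With r = 0.3 against 0 it is 0.3 × 0.4237 = 0.127 SD. Equal counts alone therefore do not clear the problem.

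**7. Sign.** If those who fall short are mainly early responders, r is negative and every sign reverses.

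**The case against.** The strongest reply is that bias is a risk here and has not been shown. It could be zero, every input above is assumed, and the largest figure needs 40% against 20% excluded with r = 0.5, which nothing in the documents supports. That stands. The case for change rests on the principle of analysing as randomised and on the absence of any unfiltered analysis to check against; it does not rest on the illustrative figures. Exclusion counts by arm would not settle the size either, since the outcomes of the excluded patients are also needed.

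A minimum number of sessions is easier to defend for therapeutic alliance and use of therapy tasks, where the SAP's target is the period of service. A patient who left early would answer the Week 8 and Week 12 surveys mostly off treatment. This also stands in part, but it does not help the Time X Condition outcomes, and even for the follow-up-only outcomes the filter selects after randomisation.

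The SAP reports no significant baseline differences. That does not show that reasons for leaving are balanced once therapy starts, and the SAP does not say whether the check was made before or after the filter.

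Removing the filter would not give a fully randomised patient comparison. Patients may consent knowing the arm, and the therapist checks eligibility knowing it. That is true, but it is no reason to add a further selection step.

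Finally, the SAP is short, written in the past tense, and reads like part of a longer account. An unfiltered analysis may exist elsewhere; none is stated in these documents.

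**Conclusion.** The concern holds. The sole stated patient analysis set is selected on attendance after therapist randomisation, and it omits patients whose follow-up the protocol requests. This must be fixed for the Time X Condition outcomes; the case is weaker, though still present, for outcomes measured only at follow-up.

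Confidence is high that the filter exists and creates the risk. The size is not known. The illustrative range runs from 0 to about 0.15 SD and assumes no true effect, the latent-propensity model, correlations up to 0.5 and the exclusion rates shown. Without a sample size or standard error, the effect on significance in this trial cannot be stated. Even if the bias is nil, the estimate describes patients who reached five sessions, whereas the SAP presents it as the effect of WILLOW.

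**What to change.** - **Main analysis set.** Take all consented patients assigned to a randomised therapist, in that therapist's arm, regardless of sessions attended. Report separately any patient who consented but was never assigned a therapist, since that patient has no arm.
- **Ineligible after the Welcome session.** The Patient Protocol (Step 5) discontinues these patients, so they may have baseline data only. State how they are handled, and give numbers and reasons by arm.
- **Model.** Use all available baseline, Week 4, 8 and 12 surveys in a likelihood-based repeated-measures model or with multiple imputation, under a stated missing-at-random assumption. Account for therapist clustering; the SAP itself reports "Design effects ranged up to 1.8".
- **Follow-up-only outcomes.** Estimate the Condition effect on all available responses, and say how responses given after therapy ended are treated.
- **Sensitivity analysis.** Keep the five-session set under that label. State whether the Welcome session counts among the five (the Therapist Protocol, Steps 7 and 12, suggests it does not), and whether the rule covers Study 1, Study 2 or both.
- **Reporting.** Give session counts, exclusions and missing surveys by arm. Session counts are already collected.

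The cost is revised SAP wording and a re-run on whatever surveys were returned. The estimated effect may be diluted, and where early leavers did not return surveys the result will rest on the missing-at-random assumption.

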PracticeGround: Transforming Training and Delivery of Mental Health EBPs

NCT02314624 | Patient Protocol | October 18, 2017

Patient Study Process overview

1. [Initial Phone Call](#)
2. [Review Screen](#)
3. [Informed Consent Call](#)
4. [Action Steps after Informed Consent Call](#)
5. (collect this date from therapist) [Welcome/Get to Know you Session](#)
6. [Scheduling Call](#)
7. [Logging Scheduling Call into Tracking DB](#)
8. [Mental Health Services Satisfaction Survey \(MSSS\)](#)
9. [Assessment Calls](#)

PI Cell Phone Numbers:

[name]: [contact]

[name]: [contact]

Step 1: Set Up Time for Initial Phone Call

1. Review clinic procedures and notes in the [Summative Tracking DB](#). Ensure they are associated with a clinic and make note of their referring provider (if indicated). If needed, find out the patient's medical record number from the referring clinic and log this in the tracking database along with the patient's name.
2. Open the [Eligibility Screen DB](#). Ensure the client is entered into the Client Referral tab.
3. Call the patient to let them know about the study and gauge their interest in participation.
4. Open the [Eligibility Screen on SurveyMonkey](#) in case patient prefers to complete screen with you over the phone.

Voice-mail Script:

Hi! This is _____ from Evidence-Based Practice Institute. I'm calling to tell you more about the research study you talked with the folks at <>Agency<> about. I would love to talk more with you about the study! I will also send you more information by email after I leave this message. Please reply to that email or call me at (phone #) when you have a few minutes to talk. Thank you!

If they call you back or pick up

Hello _____. My name is _____ and I'm calling from Evidence-Based Practice Institute. I'm calling to tell you more about the study and see if you might be interested in participating. I expect this call will take about 15 minutes. Is now a good time to talk?

WILLOW Full RCT Patient Protocol

If it is, proceed.

If not, schedule a time to call back later. Log call time and date in the Pilot RCT Calendar.

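### The SAP reports finished analyses and does not show that its choices were fixed before the data were seen; the data-derived clustering decision alone can take an assumed 5% test to about 14%.

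*SAP*

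**What the plan says.** The SAP's Analysis Strategy, dated February 8, 2020, describes completed work: "We conducted all analysis in IBM SPSS V19". It then states: "Preliminary analyses provided important information guiding our strategy". Two preliminary analyses are named.

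- A comparison of conditions at baseline: "First, we found no statistically significant differences between conditions on baseline measures".
- Design effects from the nested design: "Design effects ranged up to 1.8". One decision is tied expressly to this result: "Because all were under 2.0, we did not adjust analyses to account for clustering effects".

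The same section limits the analyses to patients with at least five sessions. It gives a rule for using Study 1 or Study 2 data from providers who took part in both. It names the Time X Condition effect, or the Condition effect for outcomes without a baseline, as the effects of primary interest. It states no alpha and no single primary outcome, and it calls the tests neither confirmatory nor exploratory.

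The two protocols are earlier: "NCT02314624 | Patient Protocol | October 18, 2017", with the same date on the Therapist Protocol. They are staff procedures and call scripts with no statistical section. On patients who leave therapy early, the script in Therapist Protocol Step 7 says: "Neither the patient nor the therapist will be removed from the study". The consent call in Patient Protocol Step 3 likewise asks for the remaining surveys whether or not treatment continues.

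**The concern.** A file titled Statistical Analysis Plan invites the reader to assume that its choices came before the data. This one is an account of what was done. By its own words the data guided the strategy, and no other document supplied shows an analysis choice fixed in advance.

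If choices were settled with trial data in view, or cannot be shown to have been settled earlier, a significant WILLOW effect is weaker evidence than the same p-value from a pre-specified test. The clustering decision adds a second problem. Therapists were randomised and patients follow their therapist's condition, so ignoring therapist clustering understates the standard error of the contrast the trial was run to estimate.

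**Working it through.** **Inputs.** From the documents: maximum design effect (DE) 1.8 (SAP); therapist-level randomisation (Therapist Protocol Steps 2 and 5; Patient Protocol Step 3); 2 to 5 patients planned per therapist (Therapist Protocol Step 2). Assumed, because not stated: two-sided alpha of 0.05, and every sample size and correlation in the simulations.

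**1. The plan's own figure.** DE = 1 + (m − 1) × ICC. Neither the ICC nor the realised cluster size m is given, so 1.8 cannot be reproduced. For the planned sizes it implies ICC = 0.8/(m − 1): 0.80 at m = 2, 0.40 at m = 3, 0.27 at m = 4 and 0.20 at m = 5.

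**2. Where each choice comes from.**

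| Choice | In the 2017 protocols? | Origin given in the SAP |
|---|---|---|
| No clustering adjustment | No | Expressly from design effects on trial data |
| Five-session minimum | No | None; stated before the paragraph on preliminary analyses |
| Study 1 or Study 2 record | No | None |
| Effect tested | No | Own rationale; not linked to preliminary results |
| Handling of baseline | No | Non-significant comparison reported; no decision said to follow |

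One choice is documented as data-derived. For the others, the documents give neither a pre-data source nor a statement that data drove them.

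**3. Size of an unadjusted test.** If the true variance of the contrast is DE times the variance used, size = 2 × [1 − Φ(1.96/√DE)].

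- DE 1.2: 1.96/1.095 = 1.789, size 7.4%
- DE 1.4: 1.96/1.183 = 1.656, size 9.8%
- DE 1.6: 1.96/1.265 = 1.550, size 12.1%
- DE 1.8: 1.96/1.342 = 1.461, size 14.4%

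**4. The rule of adjusting only when the estimated DE reaches 2.** Simulated under no effect, with 15 therapists per arm and 20,000 runs per setting:

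| Patients per therapist | Rule, true DE 1.4 | Rule, true DE 1.8 |
|---|---|---|
| 2 | 9.7% | 14.7% |
| 3 | 9.7% | 13.0% |
| 5 | 9.4% | 11.8% |

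A test on therapist means, used always, rejected 4.7% to 5.1%. With two patients per therapist, DE = 1 + ICC cannot exceed 2, so the rule can in effect never call for adjustment.

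**5. The baseline look.** Change scores were used if the baseline test was non-significant and baseline-adjusted analysis otherwise (40 per arm, correlation 0.3 to 0.7, 20,000 runs each). The size was 4.1% to 4.8%. This look does not inflate the error rate.

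**6. Illustration for choices with no stated origin.** Assume 80 patients, sessions spread evenly over 1 to 12, an alternative record for 20%, correlation 0.5, one outcome, no clustering and no effect. Suppose the smallest p-value were reported. In 4,000 runs the fixed analysis rejects 4.6%. Leaving the cut-off open (1, 3, 5 or 7 sessions) gives 10.2%; adding the choice of record gives 15.7%; adding change score or baseline adjustment gives 22.4%. These figures rest on assumed inputs and on selection that the documents do not report. They are not an upper bound: further outcomes or the clustering choice could raise them.

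**The case against.** The strongest reply is that the SAP hides nothing. It says that preliminary analyses guided it, never claims pre-specification, and uses primary interest only to say which model term carries the WILLOW effect. Its reference to something previously mentioned, and its undefined Study 1 and Study 2, suggest an excerpt from a longer report, so an earlier plan may exist. This stands in part: it supports saying that pre-specification is not shown, and does not support saying that none took place.

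A second reply is that the 14% belongs to the method, not to its timing, since an unadjusted test would be too liberal even if fixed in advance. That is correct. The figure measures what the one documented data-derived choice costs; it does not price having looked.

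Three stronger readings are tempting and are not supported.

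- A reader might infer that outcomes were compared by condition and the most favourable version kept. The only comparison by condition that the SAP reports among its preliminary analyses is at baseline. The design effects are not described as by-condition.
- A reader might infer that the baseline look itself spoils the error rate. Step 5 shows that it does not.
- A reader might infer that the five-session minimum breaks a 2017 analysis commitment. The Step 7 script concerns staying in the study, completing surveys and being paid. It does not define an analysis set or show when the cut-off was chosen.

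**Conclusion.** The point holds in limited form. The SAP is retrospective, and the documents do not show that any of its analysis choices came before the data. The clustering decision was, in the SAP's own words, taken from the trial data. The five-session minimum and the record rule have no earlier source here, but are not said to be data-driven.

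A nominal error rate therefore cannot be assured. The calculable part is about 14% in place of an assumed two-sided 5%, for an outcome at the stated maximum design effect of 1.8 and where that effect bears fully on the contrast. This applies most directly to the Condition effects. It may be smaller for Time X Condition, and it is smaller for outcomes with lower design effects. The 10% to 22% selection figures only illustrate what open choices could do and should not be quoted as the trial's error rate.

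**What to change.** 1. State in the SAP that it was finalised after baseline comparisons by condition and design effects had been examined.
2. For each choice in the table, give the date it was fixed and what had been seen by then. Label the tests post hoc or exploratory wherever no dated pre-data source can be shown.
3. Beside the chosen analysis, report the WILLOW effect and interval (a) with therapist clustering accounted for, (b) for all enrolled patients with data regardless of sessions attended, and (c) with the alternative Study 1 or Study 2 record where both exist.

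There is no need to require that an effect hold under every setting before it is claimed. That would let a weaker analysis veto a sound one.

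The cost is wording and re-running models on existing data. Surveys were requested from early leavers, so (b) needs no new collection. The downside is less favourable, exploratory claims and wider intervals: at a design effect of 1.8 the standard error rises by a factor of √1.8 = 1.34, about 34%. If an earlier dated plan exists, producing it removes the need for the label on the choices it covers.
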